5.2. Determination of Sample Size

Approximately 288 patients (144 in baricitinib, 144 in placebo) will provide:

- 99% power to detect a difference between the baricitinib and placebo treatment groups in ACR20 response rate (60% versus 35%) at Week 12 based on a 2-sided chi-square test at a significance level of 0.05.

The sample size and power estimates were obtained using nQuery® Advisor 7.0.

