6.10. Treatment Exposure

Duration of exposure to each study drug will be summarized for the safety population using descriptive statistics (n, mean, SD, minimum, median, maximum). Cumulative exposure and duration of exposure will be summarized in terms of frequency counts and percentages by category and treatment group.

Overall exposure will be summarized in total patient-years which are calculated according to the following:

Exposure in patient-years = sum of duration of exposure in days (for all patients in treatment group) / 365.25.

The summary for the first database lock (end of Part A) will include exposure to each treatment plus exposure for the subset of patients who are rescued during Part A from each randomized therapy.

The summary for the final lock (end of Parts A and B) will include all exposures for patients randomized to baricitinib and placebo, plus all exposures subsequent to rescue or switch to baricitinib. For the baricitinib treatment group, exposure will be calculated including the subset of patients who are rescued.

Duration of exposure will be calculated as follows:

1. Baricitinib group:

- Duration of exposure to baricitinib excluding exposure after the initiation of rescue therapy will be calculated as: [date of last study drug treatment prior to rescue – date of first study drug dose (Visit 2) + 1].
- Duration of exposure to baricitinib after the initiation of rescue therapy will be calculated as: (date of last study drug treatment – date of first baricitinib dose as rescue therapy + 1).

2. Placebo group:

- Duration of exposure to placebo excluding exposure after the initiation of rescue therapy will be calculated as: [date of last study drug treatment prior to rescue – date of first study drug dose (Visit 2) + 1].
- Duration of exposure to baricitinib after the initiation of rescue therapy will be calculated as: [date of last study drug treatment – date of first baricitinib dose as rescue therapy + 1].
- Duration of exposure to baricitinib after switch will be calculated as: (date of last study drug treatment (before rescue, if applicable) – date of first dose of study drug after switch + 1).

Summaries of treatment exposure will also include all baricitinib exposures.

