Further, for some AEs of interest, duration of the TEAE may be summarized or listed within patient AE listings. The duration of each event will be defined as the end date of AE minus the start date of treatment-emergence of the AE plus 1 day. If an AE has not ended by the date of study drug discontinuation, early discontinuation of the study/period, or completion of the study, it will be censored as of that appropriate final date.

In general, summaries of TEAEs, SAEs, AEs that lead to discontinuation from the study, and AEs that lead to temporary interruption or permanent discontinuation of study drug will include the number of patients in the safety population (N), frequency of patients experiencing the event (n), and percent of patients experiencing the event ($n/N \times 100$), and the exposure-adjusted incidence rate (EAIR). The EAIR will be expressed as the number of patients experiencing an

AE (n) per 100 patient years of exposure to treatment and is derived as 100 times the number of patients with the event divided by the sum of all patient exposure times (in years) to the treatment for the study/period. For any events that are gender-specific based on the displayed PT, the denominator used to compute the percentage will only include patients from the given gender. Treatment comparisons between treatment groups will be made using the Fisher exact test.

In an overview table, the number and percentage of patients in the safety population who experienced a death, a serious adverse event (SAE) (International Conference on Harmonisation [ICH]-defined, protocol-defined, and ICH- or protocol-defined), discontinuation from the study due to an AE or death, permanent discontinuation from study drug due to an AE or death, temporary interruption from study drug due to an AE, temporary interruption of study drug due to a lab abnormality, a TEAE, a TEAE rated as severe, or an AE possibly related to study drug based on the opinion of the investigator will be summarized by treatment.

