6.14.1.1. Common Adverse Events

The number and percent of patients with TEAEs, including the EAIR, will be summarized by treatment group using MedDRA PT nested within SOC for common TEAEs (ie, TEAEs that occurred in $\geq 2\%$ (before rounding) of any treatment group. Events will be ordered by decreasing frequency in the baricitinib group (or combined baricitinib group, where appropriate) within alphabetical SOC.

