6.14.4.8. Malignancies

Malignancies will be identified using terms from the malignant tumours SMQ (SMQ 20000194).

A by-patient listing for all patients having a malignancy event at any time will be provided and will include the information whether or not the event is considered as SAE, its relatedness to study drug, and whether or not it led to discontinuation from the study, led to permanent study drug discontinuation, or led to temporary study drug interruption.

If the number of events in the study warrants a table summary, the number and percent of patients with TEAEs associated with malignant tumors will be summarized by treatment group using MedDRA PT. Events will be ordered by decreasing frequency in the baricitinib group (or combined baricitinib group, where appropriate). Additional summaries will give an overview of malignancies. First, the total number of patients with malignant tumors which are SAEs by ICH GCP or by protocol, by ICH GCP, and by protocol only, will be provided. Second, the number of patients with TEAEs associated with malignant tumors that were rated as severe, and that were considered related to study drug in the opinion of the investigator, will be provided. Third, the number of patients with TEAEs associated with malignant tumors that led to discontinuation from the study, that led to permanent study drug discontinuation, and that led to temporary study drug interruption will be provided. EAIR will also be calculated for each PT. Tumors that are gender-specific, based on PT, will have the denominators limited to patients of that gender. Treatment comparisons may be made using the Fisher exact test.

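### SAP 6.14.1 limits the percentage, but not the exposure-adjusted incidence rate, to the relevant sex for gender-specific events, so those rates come out too low

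*SAP*

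**What the plan says.** SAP 6.14.1 says that summaries of TEAEs, SAEs, and AEs leading to study discontinuation, drug interruption or permanent drug discontinuation will generally show N, n, the percentage and the EAIR. The EAIR is the count of affected patients, scaled by 100 and "divided by the sum of all patient exposure times (in years) to the treatment for the study/period". The sentence after that definition covers events that only one sex can have: "the denominator used to compute the percentage will only include patients from the given gender". It does not mention exposure time.

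SAP 6.10 defines patient-years the same way, over the whole group: "Exposure in patient-years = sum of duration of exposure in days (for all patients in treatment group) / 365.25".

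SAP 6.14.1.1 carries the EAIR down to preferred-term level for common events: "The number and percent of patients with TEAEs, including the EAIR, will be summarized by treatment group using MedDRA PT nested within SOC".

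The malignancy section, SAP 6.14.4.8, is worded differently. It says "EAIR will also be calculated for each PT", and the next sentence reads "Tumors that are gender-specific, based on PT, will have the denominators limited to patients of that gender". That restriction is not confined to the percentage.

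**The concern.** Having defined two statistics with two denominators, 6.14.1 corrects only one of them for gender-specific terms. A programmer who follows the text will divide by everyone's patient-years. In a row for a female-only or male-only term, the percentage then describes one sex while the EAIR beside it describes both.

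What is at stake is the level of a reported safety rate. SAP 6.14 plans no formal comparisons for the summaries that bring in Part B or pool all baricitinib exposure. Time on drug differs between the cohorts in those summaries, so there the EAIR is the figure that adjusts for it. A gender-specific tumor could also appear in the general TEAE or SAE tables under one rule and in the malignancy table under another, with two different rates for the same event in one report.

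**Working it through.** **Inputs.** The documents state no EAIR and no planned sex split, so there is no figure of the plan's own to reproduce. From the documents:

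- EAIR denominator: all patients' exposure (SAP 6.14.1, and 6.10 for patient-years).
- Group size for illustration: 144 per arm (SAP 5.2: "Approximately 288 patients (144 in baricitinib, 144 in placebo) will provide").
- Both sexes are eligible (Protocol 8.1.2, criteria 36 and 37 set contraception rules for women and for men).

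Assumed: the share of exposure held by women, shown as a range.

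**Formula.** Let n be patients with the event, PY the patient-years of the whole group, and s the relevant sex's share of PY.

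- As written: 100 × n / PY
- Sex-restricted: 100 × n / (s × PY)
- As written ÷ sex-restricted = s

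Since s is below 1 whenever both sexes contribute exposure, the as-written rate is always the lower one. The shortfall is 1 − s.

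| Women's share of exposure (assumed) | Female-specific EAIR too low by | Male-specific EAIR too low by |
|---|---|---|
| 50% | 50% | 50% |
| 60% | 40% | 60% |
| 70% | 30% | 70% |
| 80% | 20% | 80% |
| 90% | 10% | 90% |

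**Example.** Take 144 patients, all exposed for 24 weeks, and 3 with the event. (3/144 = 2.1%, just above the 2% threshold for common TEAEs.)

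- PY = 144 × 24 × 7 / 365.25 = 66.2
- EAIR as written = 300 / 66.2 = 4.53 per 100 patient-years
- With 80% women, female-specific term: 4.53 / 0.80 = 5.66
- With 80% women, male-specific term: 4.53 / 0.20 = 22.65

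**Consistency within the row.** Dividing the percentage by the EAIR should return mean exposure per patient in years. For the female-specific term, the restricted percentage is 3 / (144 × 0.80) = 2.60%. With the restricted rate, 2.60 / 5.66 = 0.46 years, or 24 weeks, as it should be. With the as-written rate, 2.60 / 4.53 = 0.575 years, or 30 weeks, which is longer than the period analysed.

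**Effect between arms.** The as-written ratio of two arms' rates equals the true ratio multiplied by the ratio of their sex shares. With 80% women in both arms the factor is 0.80/0.80 = 1.00, so nothing changes. With 84% against 76% women, the factor for a male-specific term is 0.16/0.24 = 0.67. At 144 per arm and 80% women overall, the standard error of the difference in the proportion of women is √(2 × 0.8 × 0.2 / 144) = 4.7 points. An 8-point gap is therefore about 1.7 standard errors (two-sided p about 0.09): possible, but larger than a typical chance imbalance.

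**The case against.** The strongest case on the other side is that this is uneven drafting in a descriptive column. Several parts of it stand.

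- **Not every sex-specific rate is affected.** A reader might infer that all of them are wrong. SAP 6.14.4.8 places its restriction directly after saying that an EAIR is calculated per term, and most naturally covers it. That reading is not certain: the plural may only reflect several tumors and groups, and the sentence speaks of patients, not exposure time. It is enough to rule out the claim that every gender-specific EAIR is too low.
- **No treatment comparison is biased.** A reader might infer this because sex is not a randomization stratum (SAP 5.3 names only country and joint erosion status). The documents plan no EAIR ratio, difference, interval or test. Comparisons use the Fisher exact test on patient counts, which does not use exposure. The 0.67 above concerns a ratio that a reader would have to form unaided.
- **The size is not known.** It rests wholly on an assumed sex mix. The large shortfalls apply to male-specific terms when men are few: 10% to 30% of 144 is about 14 to 43 men per arm, so such rates would usually rest on very few events.
- **The rows affected are few.** The count and a correctly restricted percentage appear beside the diluted rate.

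What does not stand is that the wording can be left as it is. No other section adds a sex restriction for non-malignancy rates, and 6.10 confirms the all-patient total. The stated rule yields a wrong number, even if only through oversight.

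**Conclusion.** The point holds, with limited reach. Gender-specific EAIRs computed under SAP 6.14.1 (TEAE, SAE, discontinuation and interruption summaries) and 6.14.1.1 (common TEAEs) are too low, and equal the correct rate multiplied by the relevant sex's share of exposure. The direction follows from the text and needs only that both sexes contribute exposure. The size depends on a sex mix that the documents do not give: for an assumed 70% to 90% of exposure in women, 10% to 30% too low for female-specific terms and 70% to 90% for male-specific terms. Tumor rates under 6.14.4.8 appear to be restricted already. The consequence is confined to descriptive rates. Severity is minor.

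**What to change.** In SAP 6.14.1, state that for gender-specific preferred terms both denominators are limited to the relevant sex: the patient count for the percentage, and the patient-years for the EAIR. In SAP 6.14.4.8, say explicitly that the existing restriction covers the EAIR as well as the percentage, so that the same event carries the same rate wherever it is tabulated. The cost is one sentence in 6.14.1, a short clarification in 6.14.4.8 and one sex filter in the EAIR program. No new data are needed.

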6.14.1.1. Common Adverse Events

The number and percent of patients with TEAEs, including the EAIR, will be summarized by treatment group using MedDRA PT nested within SOC for common TEAEs (ie, TEAEs that occurred in $\geq 2\%$ (before rounding) of any treatment group. Events will be ordered by decreasing frequency in the baricitinib group (or combined baricitinib group, where appropriate) within alphabetical SOC.

6.14.1.2. Serious Adverse Events

Consistent with the ICH E2A guideline, an SAE is any AE that results in 1 of the following outcomes:

- Death
- Initial or prolonged inpatient hospitalization
- A life-threatening experience (ie, immediate risk of dying)
- Persistent or significant disability/incapacity
- Congenital anomaly/birth defect
- Considered significant by the investigator for any other reason.

In addition, if any patient experiences an AE that requires permanent discontinuation from study drug, for an AE or abnormal laboratory result, that AE or abnormal laboratory value will be reported as an SAE (reported as 'Other reason serious'). These protocol-defined specific SAEs were defined as an AE or laboratory value that results in permanent study drug discontinuation or discontinuation from the study. These will be distinguished from ICH-defined SAEs using a scripted Clinical Data Question and Answer (CDQA) form to be completed by the investigator. The CDQA form will be sent as a query to the investigative site whenever an SAE is designated as serious based only on 'other reason serious.' The site will provide a response that will explain if the SAE was serious by conventional ICH criteria or if it was designated as serious only by the protocol requirement. In the absence of a CDQA response, the SAE cannot be considered as serious only by the protocol requirement and will be included in SAEs that are serious according to conventional ICH criteria.

The number and percent of patients who experienced any SAE (also ICH-defined and protocol-defined SAE) will be summarized by treatment group using MedDRA PT nested within SOC. Events will be ordered by decreasing frequency in the baricitinib group (or combined baricitinib group, where appropriate) within alphabetical SOC. Serious AEs overall and of each type will be summarized by treatment period and during the post-treatment follow-up period. An individual listing of all SAEs will be provided.

6.14.1.3. Other Significant Adverse Events

The number and percent of patients who discontinued from the study because of an AE or death, the number and percent of patients who permanently discontinued study drug because of an AE or death, and the number and percent of patients who temporarily interrupted study drug because

of an AE will be summarized by treatment group using MedDRA PT nested within SOC. Events will be ordered by decreasing frequency in the baricitinib group (or combined baricitinib group, where appropriate) within alphabetical SOC.

Individual listings of all AEs leading to study discontinuation and to permanent discontinuation from the study drug will be provided. A listing of all temporary study drug interruptions, including interruptions for reasons other than AEs, will be provided.

6.14.2. Vital Signs and Physical Characteristics

Vital signs and physical characteristics include systolic blood pressure (SBP), diastolic blood pressure (DBP), pulse, weight, BMI, and waist circumference. Triplicate assessments of SBP and DBP are collected at each visit. When replicate assessments are recorded on the eCRF, the average will be derived; otherwise, the average which is recorded on the eCRF will be used for the summaries. Only the average across the replicates or the average recorded on the eCRF will be analyzed. When these parameters are analyzed as continuous variables at each visit, unscheduled measurements will be excluded. When these parameters are analyzed as categorical outcomes, as treatment-emergent abnormalities, and/or as continuous variables ignoring the visit (ie, change from minimum or maximum baseline value to minimum or maximum value during the treatment period), scheduled and unscheduled measurements will be included.

In general, vital signs and physical characteristics will be summarized with descriptive statistics (n, mean, SD, minimum, median, and maximum). Summaries will be provided for baseline and for each postbaseline visit by treatment group, including change from baseline and percent change from baseline. These summaries will be based on patients who have both baseline and at least 1 postbaseline assessment.

In addition, 3 approaches to the evaluation of change from baseline will be taken:

- Change from baseline to last observation during the treatment period considering baseline as the last non-missing observation from the baseline period;
- Change from baseline to the minimum value during the treatment period considering baseline as the minimum value of the non-missing observations in the baseline period;
- Change from baseline to the maximum value during the treatment considering baseline as the maximum value of the non-missing observations in the baseline period.

Change from baseline in vital signs and physical characteristics parameters, using each approach above, will be summarized using standard descriptive statistics by visit through Week 52.

The number and percent of patients with treatment-emergent high or low vital signs and weight at any time may be summarized by treatment group.

The treatment-emergent high or low vital signs and weight outcomes are:

- A treatment-emergent **high** result is defined as a change from a value less than or equal to the high limit at all baseline visits to a value greater than the high limit at any time that meets the specified change criteria in [Table 6-2](#) during the treatment period.

- A treatment-emergent **low** result is defined as a change from a value greater than or equal to the low limit at all baseline visits to a value less than the low limit at any time that meets the specified change criteria in [Table 6-2](#) during the treatment period.
- Treatment-emergent weight gain/loss is based on percent increase/decrease from baseline.

The number and percent of patients with treatment-emergent high or low vital signs may be further summarized in terms of shift tables by time point and last visit and by treatment group. Only scheduled measurements will be included in these analyses.

[Table 6-2](#) defines the low and high baseline values as well as the criteria used to define treatment-emergence based on post-baseline values.

Table 6-2. Categorical Criteria for Abnormal Treatment-Emergent Blood Pressure and Heart Rate Measurement, and Categorical Criteria for Weight Changes for Adults

Parameter	Low	High
SBP (mm Hg) (sitting)	≤90 (low limit) and decrease from lowest value during baseline ≥20 if >90 at each baseline visit	≥140 (high limit) and increase from highest value during baseline ≥20 if <140 at each baseline visit
DBP (mm Hg) (sitting)	≤50 (low limit) and decrease from lowest value during baseline ≥10 if >50 at each baseline visit	≥90 (high limit) and increase from highest value during baseline ≥10 if <90 at each baseline visit
Heart rate (bpm) (sitting)	<50 (low limit) and decrease from lowest value during baseline ≥15 if ≥50 at each baseline visit	>100 (high limit) and increase from highest value during baseline ≥15 if ≤100 at each baseline visit
Weight (kg)	(Loss) decrease ≥7% from lowest value during baseline	(Gain) increase ≥7% from highest value during baseline

Abbreviations: bpm = beats per minute; DBP = diastolic blood pressure; SBP = systolic blood pressure.

6.14.3. Laboratory Measurements

All laboratory tests will be presented using Système International of units (SI units). For topics of safety in special groups and circumstances, laboratory test units will be specified for each analysis.

Lilly large clinical trial population based reference limits (Lilly-defined; LCTPB) will be used to define the low and high limits since it is generally desirable for limits used for analyses to have greater specificity (identify fewer false positive cases) than reference limits used for individual patient management. For the hepatic laboratory assessments (ALT, AST, total bilirubin, and alkaline phosphatase [ALP]), central laboratory reference ranges (Quintiles) will be used and all results pertaining to these assessments will be included as a separate analysis to address the risk of liver injury as a special safety topic (see [Section 6.14.4.1](#)). Central laboratory reference ranges (Quintiles) will also be used to evaluate immunoglobulins (see [Section 6.14.3](#)).

The ratio of the low-density lipoprotein (LDL) cholesterol value to the high-density lipoprotein (HDL) cholesterol, referred to as the LDL/HDL ratio, will be derived for each patient at each visit where both values are simultaneously available. This lab parameter was not included in the standard lab processing for the Phase 3 RA studies and, as such, will not have valid reference

ranges for comparison of the ratio to a standard for characterization as treatment-emergent abnormal.

Change from baseline to last observation for laboratory tests will be summarized for patients who have both baseline and at least 1 postbaseline result. Baseline will be the last nonmissing observation in the baseline period prior to receiving the first dose of the study drug. The last nonmissing observation in the treatment period will be used for this analysis. Unscheduled measurements will be excluded.

Change from the minimum value during the baseline period to the minimum value during the treatment period for selected laboratory tests will be summarized for patients who have both baseline and at least 1 post-baseline result. Baseline will be the minimum of non-missing observations in the baseline period. The minimum value in the treatment period will be used for this analysis. Similarly, change from the maximum value during the baseline period to the maximum value during the treatment period for selected laboratory tests will be summarized for patients who have both baseline and at least 1 post-baseline result. Baseline will be the maximum of non-missing observations in the baseline period. The maximum value in the treatment period will be used for this analysis. Original-scale data will be analyzed. Scheduled and unscheduled measurements will be included.

The change from baseline in laboratory assessments, using each of the 3 approaches above, will be summarized using standard descriptive statistics.

In addition, laboratory assessments will be summarized with descriptive statistics (n, mean, SD, minimum, median, and maximum) by time point. Summaries will be provided for baseline and for each postbaseline visit by treatment group, including change from baseline and percent change from baseline. These summaries will be based on patients who have both baseline and at least 1 postbaseline assessment.

The number and percent of patients with treatment-emergent abnormal, high, or low laboratory results at any time will be summarized by treatment group.

- A treatment-emergent **abnormal** result is defined as a change from normal at all baseline visits to abnormal at any time during the treatment period.
- A treatment-emergent **high** result is defined as a change from a value less than or equal to the high limit at all baseline visits to a value greater than the high limit at any time during the treatment period.
- A treatment-emergent **low** result is defined as a change from a value greater than or equal to the low limit at all baseline visits to a value less than the low limit at any time during the treatment period.

Scheduled and unscheduled measurements will be included in analysis of treatment-emergent abnormal, high, or low laboratory results. Differences between treatments (when appropriate) in incidence of treatment-emergent abnormal, high, or low laboratory results will be assessed using the Fisher exact test.

Change from study baseline to final treatment visit, from final treatment visit to follow-up visit, and from study baseline to follow-up visit in laboratory assessments will be summarized using

standard descriptive statistics. The number and percent of patients with treatment-emergent high, normal, or low laboratory results will be further summarized comparing study baseline to last follow-up visit and follow-up baseline to last follow-up visit by treatment group.

Individual listings of laboratory results which include hematology, chemistry, urinalysis, and immunoglobulin will be provided. Additional listings that restrict to abnormal results will also be provided for both the treatment period and the post-treatment follow-up period. All lab listings will be performed using SI units.

